attendance. The CHW will likewise complete an exit survey to solicit feedback for improvement. Study staff will present de-identified results to a Latino/HIV oriented community advisory board, to discern the need for iterative revisions of the intervention manual and intervention design. Study staff will make revisions to the questionnaire content to account for participant feedback on acceptability of the content and feasibility based on duration to complete the questionnaire. We estimate a need to enroll 100 individuals to randomize 75. Estimated conservative rate of attrition is 30%. This sample size is consistent with recommendations for randomized pilot studies for preliminary estimation of effect sizes and lower bounds. The primary purpose of our pilot is to determine the feasibility of the intervention program and evaluation protocols, including treatment acceptability, data collection procedures, and expected eligibility, recruitment time and effort, and follow-up rates. Given the small sample size, we will not be able to determine intervention efficacy; rather, our analyses will be mainly descriptive and will focus on confidence interval estimation. The primary focus is to assess feasibility and acceptability of the CHW+*telenovela* intervention and its impact on retention in care. Study staff will measure attended HIV primary care visits over weeks 0-16 and 17-32 weeks as well as CD4 and HIV RNA from the electronic medical record at week-24 and week-48, to assess short and long-term effects of the intervention. To obtain further information on feasibility and acceptability of the instruments at baseline and exit assessment and interview visits, study staff will present portions of the questionnaires to a focus group of Latino HIV peer workers with extensive experience working with the population, drawn from local HIV-related community advisory boards or AIDS service organizations. Study staff will present instruments to the group and perform cognitive debriefing to ascertain if the items are conveying the intended meaning. We will also receive additional feedback on acceptability of format and content. We will also ask work with these community colleagues to perform back translation from Spanish to English on items created by the study team to confirm preservation of content. We will reimburse these individuals each for \$40 for two hours of service.

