**Data analysis:** We will compare baseline distributions of key demographic and outcome variables for comparability between intervention and control groups using nonparametric tests. The pre-specified primary outcome was retention in care. We defined this outcome as having at least one visit attended in HIV clinic at both time periods (weeks 1-16 and 17-32) post-randomization. These definitions are consistent with consensus guidelines on visit consistency. Two study staff blinded to randomization allocation, extracted HIV primary care appointment history from the medical record with disagreements reconciled by a third reviewer. An HIV primary care appointment was defined as an appointment with an HIV provider, meaning a health care provider (e.g., physician or mid-level provider) who could prescribe antiretroviral treatment. The prespecified secondary outcomes were proportion with viral suppression (HIV RNA<200 copies/ml) and change in CD4 count (cells/microliter) from baseline to weeks-24 and -48 post-randomization, extracted from the medical record. Obtaining a measure of effect size may not be justified given the limited sample size but we will use these data to inform power calculations for a subsequent large-scale trial with attention to matched-arms in an R01. Participant sociodemographic and clinical characteristics were summarized by intervention allocation with Chi-square tests and t-tests. The primary outcome of RIC and secondary outcomes of viral suppression and CD4 count at weeks-24 and -48 were compared by group using Chi-square tests. Statistical significance was defined by two-sided  $p \leq 0.05$ . Analyses were conducted using SAS version 9.4 (SAS Institute, Cary, NC).

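### CD4 is assigned a Chi-square test with no categories defined, on a variable that is not the stated outcome, and the outcome analysis does not carry through the plan's estimation aim

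*Combined protocol and SAP*

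**What the plan says.** The document has one Data analysis section. It defines the CD4 outcome as "change in CD4 count (cells/microliter) from baseline to weeks-24 and -48 post-randomization", extracted from the medical record. Its account of the tests then says that the "secondary outcomes of viral suppression and CD4 count at weeks-24 and -48 were compared by group using Chi-square tests"; retention is tested in the same way. The decision rule follows: "Statistical significance was defined by two-sided" p of 0.05 or less. The section also names t-tests and nonparametric tests, but only for participant characteristics and baseline comparability.

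On estimation, the same section says "Obtaining a measure of effect size may not be justified given the limited sample size" and goes on to say that "we will use these data to inform power calculations for a subsequent large-scale trial".

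The text on sample size and purpose, under Intervention evaluation, takes a different line. It accepts that the pilot cannot establish efficacy, states that "our analyses will be mainly descriptive and will focus on confidence interval estimation", and supports the number randomised with "This sample size is consistent with recommendations for randomized pilot studies for preliminary estimation of effect sizes and lower bounds".

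**The concern.** There are two problems, and the first is the firmer.

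**CD4.** A Chi-square test compares counts in categories. CD4 count and CD4 change are both continuous, and no CD4 category appears anywhere in the document; its only laboratory threshold is the HIV RNA limit of 200 copies/ml for viral suppression. The test cannot be sensibly run without a cut-off that the plan does not state. In addition, the variable named for testing (count at each week) is not the variable named as the outcome (change from baseline).

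**Estimation.** The outcome analysis names no effect measure and no interval for any outcome, although the sample-size text rests on both. A later power calculation needs a control-arm rate and a plausible range of difference for the binary outcomes, and an SD and mean difference for CD4. A p-value supplies none of these. For the binary outcomes the loss can be made good if counts per arm are reported. For CD4 it cannot, because a Chi-square result gives neither the mean difference nor the SD.

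**Working it through.** **Inputs.** From the document: 75 to be randomised, 30% attrition, two-sided 0.05. Not in the document, so assumed: allocation of 38 v 37, retention counts, and normally distributed CD4 values with equal SD in the two arms. The sample size is supported by reference to pilot-study recommendations, with no power or precision formula, so there is no stated figure to reproduce.

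**1. Chi-square on ungrouped CD4.** Suppose all 75 values are distinct, with n1 = 38 and n2 = 37. Each value is then its own column with a single count.
- A column from arm 1 contributes (1 − n1/N)²/(n1/N) + n2/N = n2/n1. The n1 such columns sum to n2.
- The arm 2 columns likewise sum to n1.
- The statistic is therefore n1 + n2 = 75 on 74 degrees of freedom, p about 0.45, whatever the CD4 values are.

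A simulation that allowed ties (assumed mean 500, SD 200, 37 v 38) agrees: about 70 degrees of freedom, and no rejection in 1,000 runs at each true difference of 0, 0.5, 0.8 and 1.5 SD. Categories are indispensable.

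**2. Chi-square on dichotomised CD4.** This used 40,000 simulated trials with a true shift of 0.5 SD and cut-offs placed relative to the control mean. The table gives the proportion with p of 0.05 or less.

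| Arms | Cut −0.5 SD | Cut 0 | Cut +0.5 SD | t-test | Cut-offs disagree |
|---|---|---|---|---|---|
| 38 v 37 | 34% | 43% | 41% | 57% | 43% |
| 27 v 26 | 24% | 30% | 30% | 43% | 37% |

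The second row applies the 30% attrition to CD4: 0.70 × 75 = 52.5, taken as 53. A repeat with a different random seed agreed to within about one percentage point.

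**3. What a mean difference would deliver.** The 95% half-width in SD units is t(0.975, n1 + n2 − 2) × √(1/n1 + 1/n2).
- 38 v 37: 1.993 × 0.2310 = 0.46 SD.
- 27 v 26: 2.008 × 0.2748 = 0.55 SD.

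The estimate is imprecise but can be reported.

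**4. What the p-value leaves out for retention.** Two assumed results, with uncorrected Pearson Chi-square and Newcombe 95% intervals:
- 32/38 v 26/37 (84.2% v 70.3%): Chi-square 2.08, p = 0.149; difference 13.9 points, interval −5.1 to 32.0.
- 27/38 v 26/37 (71.1% v 70.3%): p = 0.941; difference 0.8 points, interval −19.2 to 20.8.

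Both are non-significant under the plan's rule, yet they would inform a later trial differently. With near-equal retention in the two arms, the Newcombe half-width is about 22 points at 50% (19/38 v 18/37), 20 at 70% (27/38 v 26/37) and 15 at 90% (34/38 v 33/37).

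**The case against.** The strongest reply concerns estimation. A reader might infer that the Data analysis section contradicts or withdraws the interval commitment. The text does not support that. The effect-size sentence is hedged, caution about effect sizes from a small pilot is sound, and naming a test does not exclude an interval. The sample-size text promises intervals in general terms, and that promise can even be read as meant for the feasibility rates. What stands is narrower: the section that should say how the outcomes will be estimated does not, and it casts doubt on an estimate that the sample-size text relies on.

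A reader might also infer that Chi-square is wrong throughout. It is a standard test for retention and viral suppression, and an interval for either follows from counts per arm. Nor does the plan say that Chi-square was applied to CD4 change: the sentence names CD4 count, and the mismatch with the outcome definition is a separate fault.

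The CD4 wording may be a drafting slip in a list of outcomes, since t-tests are named in the sentence before. The documents cannot settle this, and a slip would still need correcting. Finally, the simulated percentages depend on assumed normality, effect and cut-offs. They show that the choice of cut-off matters, not how much it mattered in this trial.

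**Conclusion.** The point holds. For CD4 it is firm and rests on the text alone: a categorical test, a continuous measure, no categories, and an analysed variable that differs from the defined outcome. Under the stated assumptions the cost at a true 0.5 SD difference is a fall from 57% of trials significant with a t-test to between 34% and 43% with a dichotomised Chi-square, and three plausible cut-offs disagree in about 43% of trials. An estimate of mean change would carry a half-width of about 0.46 SD, or 0.55 SD if the 30% attrition applied to CD4.

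For retention and viral suppression the point is one of tension and omission, and it is minor if counts per arm are reported. The feasibility aim, which the plan calls the pilot's primary purpose, is unaffected. This should be fixed, but it does not undermine the trial.

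**What to change.** In the Data analysis section:

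1. Replace the Chi-square test for CD4 with the between-arm difference in mean change from baseline at weeks 24 and 48, with its 95% interval and the SD. If results have already been seen, mark this as an addition. If a Chi-square test has already been run, state the categories used.
2. For retention and viral suppression, keep the Chi-square tests but add the risk difference with a 95% interval (Newcombe or Miettinen-Nurminen), by assigned arm, with the number missing shown for each arm.
3. Label the p-values exploratory, and reword the effect-size sentence to say that estimates will be imprecise and will be reported with intervals.

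The cost is rewording one section and a little more tabulation from data already extracted. The design and the primary outcome stay as they are. Because part of the section is in the past tense, the intervals would be added to any comparisons already made. The downside is that the report would make no claim of a statistically significant effect, which fits the plan's own statement that efficacy cannot be determined.

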### **Study protocol**

**Randomization:** At baseline we will randomly assign participants through computer-generated allocation sequence. We anticipate minimal risk of contamination but will survey participants about whether they have discussed the intervention with other participants. We considered alternative designs, including a waitlist control condition or an active treatment arm without the *novela* but these were deemed impractical for the pilot intervention.

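### Viral suppression is compared between arms without using baseline suppression; the test is valid, but stratifying on that value would tighten the estimate at almost no cost

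*Combined protocol and SAP*

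**What the plan says.** The Data analysis paragraph sets one method for retention, suppression and CD4: "secondary outcomes of viral suppression and CD4 count at weeks-24 and -48 were compared by group using Chi-square tests". It names no covariate, stratum or regression model. CD4 is defined as a change from baseline, so it has a baseline reference. Suppression is a follow-up proportion (HIV RNA below 200 copies/ml) and has none.

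Two sentences in the same paragraph deal with baseline comparability. The first reads "We will compare baseline distributions of key demographic and outcome variables for comparability between intervention and control groups using nonparametric tests". The second reads "Participant sociodemographic and clinical characteristics were summarized by intervention allocation with Chi-square tests and t-tests". Neither says what follows if the arms differ.

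The Randomization paragraph says only that "At baseline we will randomly assign participants through computer-generated allocation sequence". It states no ratio, blocking or stratification. On size, the Intervention evaluation paragraph says "We estimate a need to enroll 100 individuals to randomize 75", and puts attrition at 30%. It also says that the pilot cannot establish efficacy and that the analysis will be mostly descriptive, centred on confidence intervals. The Data analysis paragraph nevertheless keeps a two-sided 0.05 threshold and intends the data to inform the power calculation for a larger trial.

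**The concern.** Whether a person is virally suppressed at entry plausibly predicts whether they are suppressed at weeks 24 and 48. With fewer than 40 per arm and no stratified allocation described, the arms can differ on that variable by chance. A comparison that ignores it carries part of the difference into the estimated effect, and its interval is wider than it need be. Intervals are what this pilot says it will focus on, and the results are meant to inform the next trial's power calculation.

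**Working it through.** **Inputs from the documents.** 75 are randomised. With 1:1 allocation, which is assumed because no ratio is stated, 75/2 = 37.5, so 38 versus 37. If the 30% attrition falls after randomisation, 75 × 0.70 = 52.5 remain, about 26 per arm. The document does not say at which stage the 30% applies. Enrolling 100 to randomise 75 is a 25% loss (100 × 0.75 = 75); 75/0.70 would need 108. There is no power calculation to reproduce.

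**Inputs assumed.** Baseline suppression p0 = 60%. Later suppression is 90% if suppressed at baseline and 50% if not. There is no treatment effect. Variations follow below.

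**1. Validity of the unadjusted test.** Null simulations of 200,000 trials per scenario at 38 versus 37, with p0 from 50% to 80%, give overall type I error of 5.1-5.4% for the unadjusted test and 4.9-5.0% for a stratified Cochran-Mantel-Haenszel test. There is no systematic error to repair.

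**2. How often the arms differ at baseline.** The SD of the baseline difference is √[p0(1 − p0)(1/38 + 1/37)]. At p0 = 60% this is √[0.24 × 0.0533] = 11.3 points. The exact binomial chance of a gap of 10 points or more, in either direction, is:

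| p0 | 38 v 37 | 26 v 26 |
|---|---|---|
| 50% | 36% | 49% |
| 60% | 35% | 48% |
| 70% | 33% | 45% |
| 80% | 30% | 38% |
| 90% | 17% | 24% |

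**3. What a gap does to the estimate.** Shift = imbalance × prognostic gap. With a 40-point gap (90% minus 50%), imbalances of 10, 15 and 20 points give shifts of 4, 6 and 8 points. With a 20-point gap (80% versus 60%) they give 2, 3 and 4. Among simulated trials at p0 = 60% where the imbalance is at least 10 points in favour of one arm, its mean is about 16.5 points, so the mean shift is about 0.165 × 40 = 6.6 points. The stratified estimate shifts by about 0 in the same trials. When the imbalance is near 20 points and baseline is strongly prognostic, the unadjusted test rejects a true null in 10-13% of trials, against 4.4-5.2% for the stratified test. Gaps of 20 points or more arise in 3-8% of trials for p0 between 50% and 80%.

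**4. Precision.** Overall later suppression is m = 0.6 × 0.9 + 0.4 × 0.5 = 0.74. The share of outcome variance explained by baseline is p0(1 − p0)(0.9 − 0.5)²/[m(1 − m)] = 0.24 × 0.16/(0.74 × 0.26) = 0.20. Simulating the Mantel-Haenszel risk difference gives a variance ratio of about 0.81, at 37 per arm and at 26 per arm alike. The unadjusted SE is √[0.74 × 0.26 × 0.0533] = 10.1 points, a 95% half-width of about 20. Since √0.81 = 0.90, stratifying brings this to about 18.

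| Scenario | Variance ratio | Variance cut |
|---|---|---|
| p0 60%, later 90% v 50% | 0.81 | 19% |
| p0 90%, later 90% v 50% | 0.88 | 12% |
| weak predictor, later 80% v 60% | 0.96-0.97 | 3-4% |

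**5. Whether the baseline tests stand in for adjustment.** At 37 per arm, 18/37 versus 26/37 suppressed, a gap of 8/37 = 22 points, gives an uncorrected Chi-square p = 0.058. A non-significant baseline test therefore does not show that the arms are close. The two baseline sentences conflict only for continuous variables (nonparametric test versus t-test). Chi-square for categorical variables fits both.

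**The case against.** The strongest reply is that nothing here is an error. Randomisation makes the unadjusted comparison valid, and its confidence interval already allows for ordinary chance imbalance. The 6 to 7 point shift applies only to trials selected for a sizeable imbalance in one direction, and it is smaller than one standard error (10.1 points). Narrowing the half-width from about 20 to 18 points changes no decision that the documents describe, in a pilot whose purpose is feasibility. All of this stands, and it is why the point is an improvement and not a correction. It does not make the point empty, because the threshold is kept and the data inform a later power calculation.

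The size also rests on rates that the documents do not give. If only 5-10% are suppressed at baseline and the prognostic gap is 10-20 points, the gain is nil (variance ratio 1.00-1.02). At 90% suppressed with 37 per arm, at least one arm has fewer than three unsuppressed participants in 47% of trials, so the strata are thin. That baseline HIV RNA is held is itself an inference from the reference to outcome variables; the Intervention evaluation paragraph names HIV RNA only at weeks 24 and 48.

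A reader might infer three stronger things that the documents do not support:

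- **That the planned analysis is biased.** It is not, averaged over randomisations.
- **That retention, the primary outcome, has the same gap.** Retention is defined as "having at least one visit attended in HIV clinic at both time periods (weeks 1-16 and 17-32) post-randomization", and no sentence says that attendance before randomisation is extracted or that it varies among participants.
- **That the baseline significance tests damage the outcome comparison.** They are a reporting matter and do not enter it.

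Finally, much of the Data analysis paragraph is in the past tense. If outcomes have been analysed, an adjusted estimate cannot be presented as pre-planned.

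**Conclusion.** The point holds for viral suppression, as a low-cost improvement in precision. The planned test is valid. It leaves unused a baseline value that the plan appears to hold, and so accepts a wider interval and more exposure to chance imbalance than necessary. With a strong baseline predictor and 60% suppressed at entry the gain is about a fifth of the variance, or a tenth of the interval width. It falls to 12% of the variance at 90% suppressed and to 3-4% with a weak predictor. These figures assume 1:1 allocation and illustrative rates, and they depend on baseline HIV RNA being available. For retention the point is conditional on data that the documents do not show to exist. The mismatch between the two baseline sentences is minor.

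**What to change.** 1. For suppression at weeks 24 and 48, report the Mantel-Haenszel risk difference with a 95% CI, stratified by baseline HIV RNA below 200 (yes/no), alongside the unadjusted difference. First confirm that the baseline value is in the dataset. If outcome data have already been analysed, label the stratified result a supporting analysis.
2. Adjust retention for prior attendance only if attendance before randomisation is confirmed to be in the extracted record and varies among participants.
3. Reconcile the two baseline sentences into one, preferably descriptive summaries by arm without tests.

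Items 1 and 3 cost a few sentences of analysis-plan text and a short rerun, provided the baseline value is held. Item 2 could require the two blinded extractors and the third reviewer to return to the records, so it should not be assumed to be free. None of the three needs new participants or visits.

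### CD4 is defined as a numeric change from baseline, but the plan compares CD4 count at weeks 24 and 48 with Chi-square tests and defines no CD4 category

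*Combined protocol and SAP*

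**What the plan says.** The Data analysis paragraph of the combined protocol and SAP states the CD4 outcome and its analysis a few sentences apart.

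- **Outcome:** "change in CD4 count (cells/microliter) from baseline to weeks-24 and -48 post-randomization", taken from the medical record. This is numeric, with units and a baseline reference.
- **Analysis:** "viral suppression and CD4 count at weeks-24 and -48 were compared by group using Chi-square tests". The same sentence covers the retention outcome.

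Other methods are named, but not for this outcome. "Participant sociodemographic and clinical characteristics were summarized by intervention allocation with Chi-square tests and t-tests" concerns participant characteristics. The nonparametric tests are there to "compare baseline distributions of key demographic and outcome variables for comparability between intervention and control groups using nonparametric tests".

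On the purpose of the analyses, the Intervention evaluation paragraph says that "our analyses will be mainly descriptive and will focus on confidence interval estimation". The Data analysis paragraph adds that "we will use these data to inform power calculations for a subsequent large-scale trial", while warning that an effect-size measure may not be justified at this sample size. For data collection, the Intervention evaluation paragraph lists "CD4 and HIV RNA from the electronic medical record at week-24 and week-48".

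**The concern.** There are two mismatches.

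1. **Test and scale.** A Chi-square test compares frequencies across categories. CD4 change is a number, and no cut-point, grouping or responder definition turns it into a category.
2. **Quantity.** The plan defines change from baseline but tests the count at each visit.

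Two things are at stake. First, a Chi-square test on CD4 does not estimate a difference in cells/microliter. It therefore serves neither the stated focus on intervals nor the planning of a larger trial, which would need the SD of CD4 and the baseline-follow-up correlation if CD4 change were used. Second, to run the named test sensibly the analyst must choose a cut-point that the plan does not give. That choice could be made after the data are seen, and the result depends on it.

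**Working it through.** **1. The text.** The plan gives no CD4 figure to reproduce, so the first check is a reading of the whole document.

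| Item | What the document gives |
|---|---|
| CD4 outcome | Change from baseline to weeks 24 and 48, in cells/microliter |
| CD4 quantity tested | Count at weeks 24 and 48 |
| Test | Chi-square |
| CD4 category | None; the only laboratory cut-off is HIV RNA below 200 copies/ml |
| t-tests | Participant characteristics only |
| Nonparametric tests | Baseline comparability only |

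Chi-square does fit retention and viral suppression, which are binary. Nothing in the document supplies another method for CD4. This settles the point; the rest is illustration.

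**2. The named test on raw counts.** With 38 and 37 simulated values (assumed SD 200, 1,000 runs), each distinct value becomes a category. There are about 71 categories, and the largest expected cell count is about 1. The test rejected in 0% of runs at true shifts of 0, 100 and 200 cells. A t-test on the same values rejected in 4.9%, 53% and 99%. The test cannot usefully be run without a cut-point.

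**3. Intervals that a numeric analysis would give.**

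*From the plan:* 75 randomized, 30% attrition, two-sided 0.05. *Assumed:* 1:1 allocation, so 38/37; attrition after randomization, so 75 × 0.70 = 52.5, taken as 26/26; SD 200 at both times; correlation r = 0.7, range 0.5 to 0.85.

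Half-width = t(0.975) × SD × k × √(1/n₁ + 1/n₂), where k = 1 for the count, √(2(1−r)) for change and √(1−r²) with baseline adjustment. Degrees of freedom are N−2, or N−3 with adjustment.

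- 38/37, count: 1.993 × 200 × 0.2310 = 92
- 38/37, change: 92.06 × √0.6 = 71
- 38/37, adjusted: 1.9935 × 200 × 0.2310 × √0.51 = 66
- 26/26, count: 2.0086 × 200 × 0.2774 = 111
- 26/26, change: 111.4 × √0.6 = 86
- 26/26, adjusted: 2.0096 × 200 × 0.2774 × √0.51 = 80

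| 95% CI half-width over r = 0.5 to 0.85 (cells) | 38/37 | 26/26 |
|---|---|---|
| Change | 92 to 50 | 111 to 61 |
| Baseline-adjusted | 80 to 49 | 97 to 59 |

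The variance ratio of change to adjusted is 2(1−r)/(1−r²) = 2/(1+r): 1.33, 1.18 and 1.08 at r = 0.5, 0.7 and 0.85.

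**4. Rejection rates if CD4 were split at the median.** Bivariate normal data, assumed difference 100 cells (0.5 SD), r = 0.7, no continuity correction, at least 10,000 replicates per setting.

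| Analysis | 38/37 | 26/26 |
|---|---|---|
| Chi-square, median split of count | 0.41 or 0.50 | 0.31 |
| Chi-square, median split of change | 0.60 or 0.68 | 0.46 |
| t-test on change | 0.78 | 0.63 |
| Baseline-adjusted | 0.84 | 0.69 |

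At 38/37 the total is odd, and the split result depends on which side the median observation is placed; both values are shown. The split tests also reject in about 6% to 7% of null trials there, against about 5% for the numeric methods, so the 26/26 column is the fairer comparison. At 26/26, over r = 0.5 to 0.85, the rates are 0.30 to 0.31 (count split), 0.30 to 0.75 (change split), 0.43 to 0.90 (t-test) and 0.53 to 0.91 (adjusted).

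**5. Dependence on the cut-point.** By normal approximation for a 0.5 SD difference in the quantity that is split, with 75 analysed, power is 40% for a median split and 33% for a cut at the control mean plus 1 SD. A numeric comparison of the same quantity has 58%.

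**The case against.** The strongest reply is that this is compressed drafting. One sentence covers three outcomes, two of them binary, and names one test. The CD4 outcome had just been defined as a change, so the later phrase can be read as shorthand for it. That is plausible, and it weakens the second mismatch as a separate defect. Comparing follow-up counts is in any case not biased under randomization; it is inconsistent with the definition and usually less precise. The reading does not help with the first mismatch, because Chi-square does not fit a numeric change either.

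Naming a test also does not prevent means, SDs and intervals from being reported. The plan commits to intervals in general, and the sentence on power calculations does not single out CD4. This stands: the SD and correlation remain computable from the extracted values, and no planning information is lost for good. The plan nonetheless does not say that they will be reported.

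The median split appears nowhere in the plan, and the SD, difference, correlation and allocation are assumed. Rejection rates also carry little weight in a pilot that says it cannot determine efficacy. All of this stands, and the figures should be read only as an indication of size.

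Finally, baseline adjustment and a rank-based check go beyond correcting the error, and extraction of baseline CD4 is already implied by the outcome definition. Both points are fair.

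**Conclusion.** The concern holds. The stated CD4 analysis does not match the stated CD4 outcome, in the test and, read literally, in the quantity compared. This rests on the text alone and needs none of the assumed inputs.

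The consequence is modest. It affects one secondary outcome in a mainly descriptive feasibility pilot and leaves the primary outcome, the sample size and trial conduct untouched. Under the assumptions above, with 26 per arm, splitting change at its median lowers the rejection rate by 0.63 − 0.46 = 0.17 compared with a t-test on the same change. The further gap down to 0.31 for the count comes from not using baseline. The more practical loss is the missing interval, which would have a half-width of about 66 to 86 cells at r = 0.7 for change or baseline-adjusted analyses across the two sample sizes. The document does not show which analysis was actually carried out.

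**What to change.** - Restrict the Chi-square test to retention and viral suppression.
- For CD4, state that the between-arm difference in mean change from baseline to week 24 and to week 48 will be reported with a 95% confidence interval. A linear model adjusting for baseline CD4 is preferable; an unadjusted difference in mean change also corrects the error, with less precision.
- Report the SD and the baseline-follow-up correlation for planning. Add a rank-based sensitivity check if CD4 is skewed.
- If a CD4 category was intended, give the cut-point before analysis and list it as an additional outcome.
- Name baseline CD4 in the extraction sentence of the Intervention evaluation paragraph, which lists only weeks 24 and 48.
- The analysis sentence is in the past tense. If the analysis has already been run, state what was done, disclose any cut-point and when it was chosen, and label a re-analysis as such.

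The cost is one sentence in the Data analysis paragraph, a word in the extraction sentence and a few lines of SAS. No data are needed beyond the baseline and follow-up CD4 values that the defined outcome already requires.
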